**A Randomized Trial of Pioglitazone for
the Treatment of Alcohol Use Disorder**
Protocol Version 1.5
2021-03-12

1. Background and Significance

1.1 Alcohol use disorders in VA: Alcohol use disorder (AUD) and heavy drinking are common among Veterans with 42.2% of Veterans having a life-time history of AUD and 14.8% screening positive for past-year probably AUD (1). AUD is associated with increased rates of accidents (2), domestic violence (3), neurocognitive impairments(4), poor medication adherence (5), increased mortality (6) and alcohol problems influence the course and treatment of many psychiatric and medical conditions (7, 8). Harmful alcohol use is common among Vietnam era Veterans (9, 10) and among returnees from Iraq and Afghanistan high rates of new onset heavy weekly drinking, binge drinking, and alcohol-related problems are reported (11). AUD is also a high cost disease within the VA. In Fiscal Year 2009, 334,130 Veterans had at least one VA encounter for an AUD. In a random sample of nearly 600,000 VA patients, Yu and colleagues found that the marginal yearly treatment cost (cost above the mean for the entire sample) associated with a diagnosis of an AUD was \$3,124 per patient (12). This marginal cost multiplied by the number of Veterans with the disorder represents over 1 billion dollars in VA costs related to alcohol use disorders per year. Although treatments for AUD have improved over the past several decades (13), more effective interventions are needed. Pharmacological treatments for AUD are infrequently used in Veterans (14) and used less often than psychosocial interventions (15). However, without pharmacological adjunct to psychosocial therapy nearly 75% of patients resume alcohol use within one year (16). **Current pharmacological treatments are only modestly effective, at best; new medications that address AUD are needed.**

1.2 Medications for the treatment of AUD: Current medications for AUD target various brain regions that are classically thought to be involved in substance abuse behavior. Some of these regions include the nucleus accumbens and ventral striatum, thought to be involved in reinforcement, the dorsal striatum involved in habit formation, the hippocampus for its role in processing drug and alcohol contexts, and the prefrontal cortex for its role in exerting executive control over these regions. Most research has focused on GABA, glutamate and dopamine receptors as pharmacological targets as the above brain regions are mostly connected by GABAergic, glutamatergic and dopaminergic projections. In addition, compounds targeting opiate receptors have also been intensively studied (17, 18). The relationship between dopamine/dopamine pathways and craving/ reward has led to the clinical development of drugs that target this neurotransmitter in alcohol dependence (19). The Food and Drug Administration (FDA) has approved several medications for alcohol use disorder: disulfiram, an aldehyde dehydrogenase blocker; naltrexone, an opioid antagonist; injectable naltrexone (long-acting) and acamprosate, a functional glutamate antagonist. A meta-analysis of disulfiram showed limited efficacy and no effect on alcohol craving (20). Naltrexone has been shown to primarily reduce drinking severity rather than promote abstinence or non-heavy drinking (21). Early studies of naltrexone found the effect size of naltrexone was modestly higher than placebo but its clinical success for promoting abstinence and reducing heavy drinking has declined since the early single site studies (22). In clinical trials people treated with naltrexone had higher rates of dizziness, nausea and vomiting (23). Finally, oral naltrexone is contraindicated in acute hepatitis, liver failure, current opioid use, or anticipated need for opioids (24). Acamprosate has been FDA approved for AUD since 2004 and is primarily used to maintain abstinence, especially after alcohol detoxification (25). The treatment effect size of acamprosate is moderate in magnitude (25) and is limited by three times per day dosing and side effects which include anxiety, diarrhea and vomiting and is contraindicated in those with severe renal impairment (23).

Another drug that has shown efficacy in AUD studies is topiramate. Topiramate is FDA-approved for use as an anticonvulsant and as a drug to prevent migraine headaches. Its proposed mechanism of action for reducing alcohol use involves dopamine and dopamine pathways responsible for craving/reward in AUD by antagonizing excitatory glutamate receptors and inhibiting dopamine release while enhancing inhibitory GABA pathways (26). An initial study reported moderate to high effect size for reducing heavy drinking and for improving abstinence (27) however a meta-analysis using seven RCT's supported only a small to moderate effect size for topiramate (28). Also, adverse effects in those treated with topiramate are common and include cognitive dysfunction, paresthesias and taste abnormalities therefore drop-outs significantly impact its efficacy (23). Finally, gabapentin and baclofen are thought to act via GABAergic pathways. Most controlled trials of gabapentin have been small and of brief duration and none have included Veterans. Anton and colleagues added gabapentin to naltrexone during the first 6-weeks of a randomized controlled trial and found that the combination improved sleep and drinking outcomes as compared with naltrexone alone (and placebo) but the effect did not endure after gabapentin was discontinued (29). Furieri and colleagues showed that gabapentin reduced alcohol craving and alcohol consumption when compared to placebo; however, the study lasted only 28 days, used low dose (300mg twice per day) gabapentin and only included 60 total subjects (30). In a dose-ranging trial, Mason and colleagues found a linear-dose response with 1800mg of gabapentin being most effective in rates of complete abstinence and no-heavy drinking over a 12-week study (31). Side effects included fatigue (23%), insomnia (18%) and headache (14%) and only 56% of the subjects completed the study which suggests a significant limitation of this medication. Baclofen, another GABAergic medication has shown mixed results. An early study by Addolorato found significant improvement in alcohol outcomes in patients with cirrhosis but the study was relatively small (32) and later studies including our CSR&D funded study did not differentiate baclofen from placebo (33, 34). Finally, one important limitation of most of these medications is that they do not influence important alcohol outcomes that are associated with improved health. Specifically, in 2015 the FDA provided guidance for the development of drugs to treat "alcoholism" and recommended using responder analyses based on definitions that predict clinical benefit rather than analyses of group means as mean differences are difficult to interpret in regard to clinical relevance. They recommend using complete abstinence and no heavy drinking for defined periods of time, as efficacy endpoints (35). A variety of data suggest that the outcome of no heavy drinking is associated with reduced alcohol consequences, reduced likelihood of meeting future criteria for AUD, reduced risk of relapse and lower rates of alcohol-related problems (35). Most AUD medication studies have not shown this level of evidence in support of their use.

In summary, these data suggest that medications to treat AUD have only small to moderate effect sizes; they are used infrequently and have limited impact on meaningful clinical outcomes that are associated with improved health. Thus, new medications with unique mechanisms of action and with improved tolerability and efficacy are needed to address AUD in Veterans.

1.3 Relevance to Veterans Health: Veterans have high rates of AUD with significant impact on health, quality of life and mortality. In addition, the direct and indirect cost of AUD are high. Current medication treatment approaches are infrequently used and of only small to modest benefit. Pioglitazone has shown promise in several pre-clinical studies but no AUD clinically focused studies are available. If pioglitazone is found to be useful in reducing or eliminating alcohol use in Veterans it could be easily and rapidly repurposed to treat AUD, as it is already an FDA approved medication. Pioglitazone, given its unique mechanism of action, may offer an innovative approach to treating Veterans with AUD and thus help reduce the impact of this costly and difficult problem.

1.4 Pioglitazone a novel treatment for AUD: Peroxisome proliferator-activated receptors (PPAR) are a group of nuclear receptor proteins that primarily regulate gene expression via their role as ligand-activated transcription factors. PPAR agonists have been shown to reduce addictive behaviors in pre-clinical models including reducing chronic alcohol intake, binge alcohol intake, stress induced relapse and withdrawal in alcohol preferring rats (36). In addition, PPAR agonists have been shown to reduce a variety of behaviors related to other drugs of abuse, including nicotine, cocaine and heroin (37). There have been three PPAR isoforms identified, alpha, delta and gamma, each transcribed from different genes. Pioglitazone is a PPAR γ agonist and has been reported to decrease voluntary alcohol consumption of a 10% alcohol solution in rats genetically selected for high alcohol consumption. In addition, when rats had to perform an operant task to receive alcohol, pioglitazone reduced alcohol self-administration but not saccharin intake. These data suggest that pioglitazone reduces the motivation to consume alcohol (38).

Peroxisome proliferator-activated receptor agonists may exert their effects on alcohol use in a variety of ways. Activation of PPAR γ has been shown to mediate neuroprotection from N-methyl-D-aspartate (NMDA) mediated excitotoxic processes and inflammatory damage (37). PPAR γ agonists also inhibit pro-inflammatory IL-1 beta, IL-6, and TNF- α production and may exert its effects via reduction in innate immune signaling (39). Peroxisome proliferator-activated receptors have been found to be expressed in neurons, oligodendrocytes, and astrocytes in the central nervous system (cite). PPAR γ are highly expressed in the lateral hypothalamus (LH), the paraventricular nucleus of the hypothalamus (PVN), the arcuate nucleus (ARC), and the ventral tegmental area (VTA). PPAR γ receptors co-localize with tyrosine hydroxylase in the VTA suggesting the expression of this receptor in dopaminergic cells and thus pioglitazone may reduce this rewarding/reinforcing effect in AUD (40-42). Although, several pre-clinical studies suggest a significant positive effect from PPAR agonists on alcohol and drug use, only one human study is available and that was focused on treating cocaine use disorder (43). The 12-week pilot study randomized 31 patients with cocaine use disorder to either pioglitazone or placebo and found a higher likelihood of reduced cocaine craving in patients treated with pioglitazone. Adherence to pioglitazone was high and side effects were mild, no serious adverse events occurred. Twenty-six subjects also met criteria for AUD and the data suggest that pioglitazone was effective at reducing alcohol use over placebo (43).

1.5 Summary of Pioglitazone pharmacological and toxicological data: Pioglitazone was FDA approved in 1999 to improve glycemic control in patients with type 2 diabetes, thus side effects and risks are well known. The FDA package insert provides information on a variety of risks and potential side effects that is summarized: The most common side effects (>5%) include upper respiratory tract infection, pharyngitis, headache, sinusitis and myalgia. Although the overall risks of these problems are greater than 5%, the risks when compared to placebo are all less than 5%. Of note, there have also been several warnings issued regarding pioglitazone. First, pioglitazone alone or more commonly in combination with other antidiabetic agents (typically insulin) can cause fluid retention and edema which increases the risk of congestive heart failure. The risk of heart failure was more common when comparing pioglitazone to placebo in a high-risk group of patients with diabetes and pre-existing cardiovascular disease (44). There have been several reports of hepatotoxicity but not enough data to establish probable causality. There was a small increased rate of fractures in women and a small increased risk of urinary bladder cancer in patients treated for 24 months or longer. Finally, pioglitazone is a category C medication and thus should not be used in pregnancy and it may also induce ovulation so individuals may be at greater risk for pregnancy when taking this medication (45).

In addition to the package insert there are a variety of published data in a diverse number of conditions including four published reports in patients treated for depression and a recent study that used pioglitazone to treat cocaine use which included 26 individuals with alcohol use disorder- see above. Studies with important safety information are summarized here: A meta-analysis of pioglitazone used for reducing liver fibrosis in nonalcoholic steatohepatitis reviewed 8 RCT's with 516 patients followed between 6 and 24 months and found weight gain and lower limb edema as the primary adverse events (46). A recently published article using pioglitazone, for 30 months, in a similar clinical population, found no difference of major drug-related adverse events with minimal weight gain being the primary difference between pioglitazone and placebo (47). Although prior retrospective studies led to the FDA boxed warning for bladder cancer, two recent prospective studies suggest no link between pioglitazone and bladder cancer (48, 49). There have been four published RCT's of pioglitazone for major depressive disorder with a total of 161 patients enrolled (6-12 week studies) with no significant adverse events occurring (50-53). Pioglitazone has also been explored as a treatment for dementia. A recent meta-analysis using PPAR- γ agonists to treat dementia found 9 studies in 4,327 participants and found no significant difference in adverse or serious adverse events (54). A recent placebo controlled trial of pioglitazone for 30 patients with cocaine use disorder of whom 26 had an AUD reported the most frequent side effects were sleep disruption, diarrhea, stomach pain, cough, and increased urination which were all rated as mild (43). Finally, a recent, very small randomized trial comparing pioglitazone to placebo in a "mechanistic proof of principle" study to determine the effect of pioglitazone on alcohol craving was stopped early after 16 subjects were randomized due to safety concerns. The study entailed two experimental manipulations designed to induce alcohol craving, guided imagery compared to intravenous lipopolysaccharide. A total of 14 subjects (6 pioglitazone and 8 placebo) were analyzed. Five in the pioglitazone arm had elevated creatine kinase (CK), one was deemed serious and one receiving placebo had an elevated CK. The study did not report absolute values for CK nor whether or how the CK was related to the initiation of pioglitazone or other whether it was temporally related to other study procedures (Schwandt et al psychopharmacology 2020). **In summary, pioglitazone is well tolerated with few side effects or significant safety concerns, particularly in short term (less than 24 weeks) studies.**

2.0 Preliminary Studies: The Minneapolis and Long Beach VAHCS have a long history of scientific collaboration. We have completed two prior CSR&D funded randomized controlled trials in AUD. The first was a RCT of motivational enhancement therapy in patients with AUD and chronic hepatitis C. We were able to show that motivational enhancement therapy helped reduce alcohol use in this population (55). The second was a placebo controlled RCT of baclofen in patients with AUD and hepatitis C. This was the largest trial of baclofen and showed no effect of baclofen on reducing alcohol use in this population (34). As previously noted there are no published trials of pioglitazone focused on AUD. However, in a preliminary investigation at the Minneapolis VA, we identified 252 patients who had at least one prescription for pioglitazone during 2016, all of these patients were being treated for diabetes. Of these 252 patients 51 had an AUDIT-C score of at least 3 prior to starting the pioglitazone. The average AUDIT-C score prior to starting pioglitazone was 4.18 (1.69) the average AUDIT-C score after Pioglitazone was started was 2.85 (1.76). Patients stopped and started pioglitazone at various times and we determined the effect of pioglitazone on AUDIT-C scores by using a mixed regression model to compare AUDIT-C scores while on pioglitazone with those scores when not on pioglitazone. This analysis suggested that pioglitazone was associated with a reduction in AUDIT-C scores ($F(1,312.2)=14.29$, $p<.001$). **These data, combined with preclinical studies and the Schmitz study of cocaine using patients, suggest that pioglitazone is an effective**

medication for AUD. A well-designed trial of pioglitazone focused on AUD is warranted and needed.

3.0 Research Design and Methods

3.1 Overview

This proposed research study is a double-blind controlled clinical trial of 200 Veterans with AUD randomized to either pioglitazone or placebo.

After screening visits and informed consent, participants who meet all inclusion and exclusion criteria and who sign the informed consent will be given a breathalyzer test and test result must be below 0.05 in order for potential participant to be enrolled (see Breathalyzer Testing section, precautions will be taken based on test result). Following the breathalyzer test, participants will complete the initial assessment instruments, which include the SCID, Obsessive Compulsive Drinking Scale (OCDS), Timeline Follow Back (TLFB), Beck Depression Inventory-2nd edition (BDI-II) and the PTSD Checklist (PCL-5). They will also provide a urine sample for a urine drug screen, Ethyl Glucuronide (EtG), and Ethyl Sulfate (EtS), and blood samples for ALT, AST and BNP. Women of childbearing potential will provide a urine sample for Beta-Human chorionic gonadotropin (β -HCG). Participants will then be randomized to receive either pioglitazone or a placebo (see **Data Analysis Plan-Randomization** section).

After randomization, all the participants will be seen weekly for the first 4 weeks (visits 1,2,3,4- baseline or randomization visit will be visit 0) then every 2 weeks until the end of the study (week 6 or visit 5, week 8 or visit 6, week 10 or visit 7, week 12 or visit 8, and week 14 or visit 9) for a maximum of 12 visits (including the screening visit, baseline visit, and closeout visit). At week 16, there will be a termination or closeout visit after study medications have been tapered. All study measures will be administered at each visit during the double-blind period from weeks 0 to 14 and week 16 or the closeout visit. In particular, the BDI-II and PCL-5, will be given at each study visit. If participants report significant depressive or other psychiatric symptoms during the study, the decision to exclude them will be based on whether they can safely participate in the remainder of the study (See **Human Subjects** section). Data will also be collected from participants' medical records regarding enrollment and attendance at specialty alcohol treatment appointments. Follow-up assessments will be conducted in person by a rater blinded to the participant's study condition.

The initial screening and baseline visit (may be done at the same time) and week 4 and 14 visits will be conducted in person. However, to enhance subject safety and minimize the risk of COVID-19, all other visits will be conducted by phone but may be conducted in person if the patient requests or if in the opinion of the PI a face-to-face visit is necessary for subject safety.

Participants will have medication adherence assessed at each study visit (total number of tablets dispensed – tablets reported taken divided by the total number of tablets dispensed taking into consideration that patients will be given additional study medication in the event of missed visits- 7 days of additional medication). Tablet counts will be confirmed at each of the face-to-face visits. Participants will have a breathalyzer test at each face-to-face visit and will not be allowed to complete assessments if their test result is above 0.05%. For phone visits, subjects will be evaluated clinically for intoxication ie coherent speech, slurred words, able to follow questions and respond appropriately.

Measure	Week	May occur at same visit		Double Blind Period										
		Screening	Baseline	Week 1	Week 2	Week 3	Week 4	Week 6	Week 8	Week 10	Week 12	Week 14	Week 16	
Informed Consent		X	X											
Eligibility Determination		X												

SCID DSM-5	X										
Randomization (pioglitazone or placebo)		X									
Demographics/ Medical History	X										
Pharmacy Dispenses Study Drug (pioglitazone or placebo)		X	X	X	X	X	X	X	X	X	
Determination of Study Drug Compliance			X	X	X	X	X	X	X	X	X
BBCET		X	X	X	X	X	X	X	X	X	
Breathalyzer	X	X	X	X	X	X	X	X	X	X	X
BSI		X	X	X	X	X	X	X	X	X	X
BDI-II		X	X	X	X	X	X	X	X	X	X
PCL-5		X	X	X	X	X	X	X	X	X	X
OCDS		X	X	X	X	X	X	X	X	X	X
TLFB	X	X	X	X	X	X	X	X	X	X	X
EtG/EtS, (Urine)		X				X					X
ALT, AST, GGTP, BNP, CK		X				X					X
CRP		X				X					X
Inflammatory markers		X				X					X
Medication side effects			X	X	X	X	X	X	X	X	X
Attendance at EtOH Tx	X		X	X	X	X	X	X	X	X	X
Urine Drug Screen, β - HCG	X										

Participants will provide a urine sample for EtG, EtS, and β -HCG (for women of childbearing potential), ALT, AST, GGTP, CK and BNP at baseline. The EtG, EtS, ALT, AST, GGTP and BNP, will be repeated at weeks 4, and 14.

3.2 Participants: Male and female Veterans above the age of 18 will be recruited from outpatient clinics at the Minneapolis and Long Beach VAHCS's and through advertisements at each site.

3.3 Screening: The AUDIT-C will be used as a method to identify potential participants. The AUDIT-C is used clinically to screen for and identify heavy alcohol use in all VA's. Patients with an elevated AUDIT-C of 4 or greater will be contacted by study staff via letter and recruited to the study. Clinical staff can also refer patients with a similar AUDIT-C or if there is concern for heavy alcohol use.

Individuals who are interested in the study will be asked if they would like to participate in a qualifying assessment. If apparently qualified and interested in participating in the study, they will be given the consent form to read by a study staff member. The study staff member will answer their questions and determine whether the individual understands the study through a series of pre-determined questions. The questions will include whether the individual understands the key tasks, risks, benefits of participating in the study as described in the consent form. If the individual understands these details and chooses to sign the consent form, they will participate in the qualifying assessment. This assessment is designed to determine if the participant fully meets the inclusion and exclusion criteria for participation in the study. The results of the assessment are reviewed by the PI to make a final determination of eligibility for the study's clinical trial. If the patient does not qualify this will be explained to the patient, they

will be paid for the qualifying assessment and given referral information if deemed appropriate by the PI.

3.4 Inclusion criteria:

- 1) DSM-5 diagnosis of at least moderate alcohol use disorder using the SCID
- 2) A mean of six heavy drinking days per month for the 3-months prior to baseline.
- 3) Drinking at least 14 drinks for men or 7 drinks for women, or more per week for the 4 weeks preceding the screening visit.
- 4) Willingness to provide contact information to confirm study follow-up appointments
- 5) Ability to perform informed consent
- 6) Female subjects: a negative pregnancy test
- 7) Serum ALT < 3 times reference range
- 8) Stable psychiatric medication doses the month prior to baseline visit (antidepressant, antipsychotic, subjects may have changes in trazodone for sleep)

3.5 Exclusion criteria:

- 1) Current DSM-5 diagnosis of moderate to severe psychoactive substance use disorder (i.e. cocaine, opiates, methamphetamine) other than cannabis or nicotine
- 2) Medical conditions contraindicating pioglitazone pharmacotherapy (e.g., congestive heart failure, clinically significant edema, clinically significant liver disease, hypoglycemia, diabetes, history of bladder cancer)
- 3) Taking medications known to have significant drug interactions with the study medication (CYP2C8 inhibitors or inducers, antihyperglycemic medications)
- 4) Cognitive or physical impairment that precludes study participation
- 5) Currently and seriously suicidal (i.e., plan and intent)
- 6) Currently being treated for AUD with a medication (naltrexone, naltrexone injectable, acamprosate, topiramate, disulfiram and gabapentin)
- 7) Impending incarceration
- 8) Pregnant or planning to become pregnant during the course of the trial or nursing for female patients
- 9) Unwillingness to sign a written informed consent form
- 10) Unwillingness to use a barrier method of birth control during the study for female patients

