3.7 Intervention

At the baseline (week 0) visit participants will be randomized to receive either pioglitazone or a matching placebo by the research pharmacist (**see Randomization section**). Participants and study personnel will be unaware of the treatment assignment. In order to maintain study blind but insure patient safety, sealed envelopes that contain the identification of the study medication (pioglitazone or placebo) will be kept in the research pharmacy and opened only in case of emergency. Study medication will be dispensed in a double-blind fashion during the entire study period. Study medication will be dispensed at baseline and weeks 1,2 and 3 sufficient for a 2-week period (taking into consideration the possibility of missed visits) and will be given at weeks 4,6,8,10, and 12 sufficient for a 3-week period (taking into consideration the possibility of missed visits). Placebo capsules will be of an identical size, shape and color as pioglitazone. Active medication will be started at 15mg per day and titrated over two weeks until reaching a target dose of 45mg per day. This is the FDA maximum dose and was selected based on a prior small study focused on the treatment of cocaine use (43).

All participants will receive Brief Behavioral Compliance Enhancement Treatment (BBCET) as their psychosocial treatment. This is a standardized 15-minute intervention that emphasizes medication adherence as a crucial element to change alcohol use behavior (56). It will be administered at every visit. BBCET has been used in previous AUD medication trials as the psychosocial treatment (27, 57). We also used the BBCET for the CSR&D funded “Efficacy & safety of baclofen to reduce alcohol use in veterans with HCV” and have extensive knowledge in delivering this intervention (34). Study staff will be trained to administer the BBCET and 2% of sessions will be observed for adherence to the intervention.

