4.6 Attrition: We anticipate an attrition rate of 20% and this has been considered when calculating the budget and in the power analysis. Rationale for this estimate includes several factors. The attrition rate in our prior studies ranged from 14% (55) to 24% (34). Second, some patients may be more interested in remaining in a medication study with high perceived efficacy. The medication will be dispensed at the outpatient clinic, which should reduce the stigma typically associated with specialty alcohol treatment. Finally, participant compensation will provide an incentive to complete the follow-up sessions. However, we have reviewed other VA alcohol treatment studies that showed great variation in attrition rates, **therefore we are projecting a conservative estimate that 80% of the participants consented will complete the study.**

4.7 Missing Data: We will perform an intent-to-treat analysis, meaning that all subjects randomized into two treatment groups will be included in the analysis regardless of the extent of compliance with the treatment or withdrawals during the trial. This will create incomplete data because some subjects will withdraw from the study during the course of the treatment, thereby their responses will be considered missing after withdrawal. **If the dropout process is related to the outcome measures (i.e., alcohol use), this will present a challenge in the analysis.** The majority of the currently available statistical methods assume that data are missing at random. However, in this study, it is plausible that the likelihood of dropout is related to the level of or change in alcohol use. For example, those with increase or no reduction in alcohol use may be more likely to drop out of the study. When subjects drop out of the study, we will attempt to obtain data on reasons for dropout. We will analyze whether the dropout process is at random with respect to the outcome measures. If the dropout process is related to the outcome measures, we will utilize models that incorporate a nonrandom dropout mechanism (Little, 1995). These analyses will be carried out as the secondary analyses for hypothesis-generating purposes. Use of the EM algorithm in the analysis will allow inclusion of observations with missing datapoints. This increases power and improves the ability to produce estimates with less bias.

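### The adherence formula in Section 3.1 runs backwards: it gives the share of tablets not taken, so a participant who takes nothing scores 100%

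*Combined protocol and SAP*

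**What the plan says.** Section 3.1 (Overview) states that "Participants will have medication adherence assessed at each study visit" and gives the calculation in parentheses: "total number of tablets dispensed – tablets reported taken divided by the total number of tablets dispensed". The same parenthesis continues "taking into consideration that patients will be given additional study medication in the event of missed visits- 7 days of additional medication", without saying how the extra days enter the calculation. It is followed by "Tablet counts will be confirmed at each of the face-to-face visits". By default the in-person follow-up visits are weeks 4 and 14; the others are by phone unless the participant asks otherwise or the investigator judges an in-person visit necessary for safety.

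Section 3.7 (Intervention) gives the supply: "Study medication will be dispensed at baseline and weeks 1,2 and 3 sufficient for a 2-week period", and study drug "will be given at weeks 4,6,8,10, and 12 sufficient for a 3-week period".

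The schedule table in Section 3.1 has a row for determining study drug compliance but no formula. Section 4.7 (Missing Data) says that all randomized subjects "will be included in the analysis regardless of the extent of compliance with the treatment or withdrawals during the trial". No section sets an adherence threshold, a per-protocol set or an adherence-based analysis.

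**The concern.** Adherence should rise as more tablets are taken. The written expression subtracts tablets taken from tablets dispensed, so it falls instead. The subtraction would be right if the subtracted quantity were tablets returned or remaining, but the text names tablets reported taken.

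The measure will be read. It is due at every follow-up visit, and the psychosocial treatment given to both arms (BBCET, Section 3.7) is built around adherence. Section 1.4 also cites high adherence in the earlier cocaine pilot. Because the main analysis ignores compliance, a null result would send readers to the adherence data to ask whether the drug failed or was not taken. A variable programmed literally from Section 3.1 would answer that question the wrong way round.

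**Working it through.** The plan states no adherence figure, so there is nothing to reproduce. The check is to evaluate the formula on the plan's own supply schedule.

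**Inputs**
- D, supply per dispensing (Section 3.7): 14 days for each 7-day interval in the weekly phase; 21 days for each 14-day interval in the two-weekly phase.
- B, reserve (Section 3.1): 7 days. This agrees with Section 3.7, since 14 − 7 = 7 and 21 − 7 = 14.
- T, days' worth of tablets taken: none, half or all of the scheduled doses.
- Assumption: tablets per day are constant within an interval, so days of supply can stand in for tablets.

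**Formula as written, (D − T)/D**
- Takes nothing: (14 − 0)/14 = 100%; (21 − 0)/21 = 100%.
- Takes every scheduled dose: (14 − 7)/14 = 50%; (21 − 14)/21 = 33%.

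**Can the reserve clause rescue it?** Each cell shows none / half / all scheduled doses taken.

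| Version | Weekly phase | Two-weekly phase |
|---|---|---|
| As written, (D − T)/D | 100 / 75 / 50% | 100 / 67 / 33% |
| Reserve out of both, (D − B − T)/(D − B) | 100 / 50 / 0% | 100 / 50 / 0% |
| Reserve out of numerator, (D − B − T)/D | 50 / 25 / 0% | 67 / 33 / 0% |
| Reserve out of denominator, (D − T)/(D − B) | 200 / 150 / 100% | 150 / 100 / 50% |
| Right way round, no reserve rule, T/D | 0 / 25 / 50% | 0 / 33 / 67% |
| Right way round, reserve removed, T/(D − B) | 0 / 50 / 100% | 0 / 50 / 100% |

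The first four rows keep the subtraction, and in all of them the score falls as intake rises. Strict operator order, D − (T/D), gives 14 or 21 for a participant who takes nothing, which is not a proportion. Only the last row behaves as an adherence measure should.

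**Conditional scenario: supplies accumulate.** If every dispensing is a full new supply and nothing is returned or netted off, total supply before week 14 is 4 × 14 + 5 × 21 = 161 days, for 98 days of use.
- As written, a perfect taker scores (161 − 98)/161 = 39%. With one 7-day allowance deducted from the total, the score is (154 − 98)/154 = 36%.
- Right way round, the same participant scores 98/161 = 61%, or 98/154 = 64% with one allowance deducted.

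In this scenario a single 7-day deduction from the cumulative total is too small. The documents do not say that this is how supply or adherence will be handled.

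**The case against.** Four points can be made for the plan.

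1. *The dash may be punctuation.* The text would then mean tablets taken over tablets dispensed, and with the 7-day reserve removed per dispensing it would be correct. But the opening reference to tablets dispensed would then do no work, and the reserve rule would still be unstated. The sentence needs repair on either reading.

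2. *The reserve is already provided for.* This stands. A reader might infer from the surplus in each dispensing that tablets dispensed is an unusable denominator in this design, or that turning the formula round could not be enough. The documents do not support that. Per dispensing, the 7-day allowance fits both phases exactly, and T/(D − B) gives 0%, 50% and 100%.

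3. *The accumulation figures are not established.* This also stands. A reader might take the 161 days and the 39%, 36% and 61% scores as what the trial will produce. They require full new supplies every time and no return or netting off, for example at the week 4 count. The documents are silent on returns and carry-over, and the supply wording could also describe topping up. Section 3.11 points away from a stockpile: it expects a participant who misses three consecutive visits to have been without drug for at least a week. That matches a single 14-day supply set against 21 days in the weekly phase (21 − 14 = 7).

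4. *Little depends on it.* Largely true. A reader might infer that the primary result or an adherence subgroup would be reversed, but the plan has no such subgroup and the main analysis disregards compliance. The raw inputs are collected and the written score is the complement of T/D, so the error can be undone later. A score of 100% for a participant known to have taken nothing would probably be noticed. That limits the harm but does not make the definition right.

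**Conclusion.** The definition is wrong as written. It measures non-adherence: 100% for a participant who takes nothing, and 50% (weekly phase) or 33% (two-weekly phase) for one who takes every scheduled dose, before any reserve adjustment. The inverted direction holds under every placement of the 7-day reserve and does not depend on whether stock accumulates. The exact percentages assume constant tablets per day within an interval. Section 3.7 describes a two-week titration and does not give tablets per day, so this may not hold early on.

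The consequence is confined to adherence reporting and the interpretation of the intent-to-treat result. No endpoint, analysis set or power figure uses adherence. The possible build-up of surplus stock is a conditional, secondary reason to prefer tablets scheduled as the denominator; it is not a demonstrated second error.

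**What to change.** Replace the parenthesis in Section 3.1 with:

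adherence = tablets taken / tablets scheduled for the days elapsed since the last assessment.

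- At phone visits, tablets taken is the self-reported number.
- At in-person counts, tablets taken = tablets on hand at the last count + tablets dispensed since − tablets remaining, with tablets scheduled covering the same period.
- Tablets scheduled should follow the trial's own dosing schedule, including the titration period. Reserve tablets then stay out of the denominator and need no separate deduction.

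The carried-forward stock must be included. In the accumulation scenario a perfect taker has 56 − 28 = 28 days left at week 4, receives 105 more, uses 70 and has 63 left at week 14. The formula gives (0 + 56 − 28)/28 = 100% at week 4 and (28 + 105 − 63)/70 = 100% at week 14. Without the stock on hand at week 4, the week 14 value would be (105 − 63)/70 = 60%.

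The cost is a few lines in Section 3.1 and the matching derivation in the analysis code. Tablet counts and self-reports are already planned, so no new visits or measures are needed; the count on hand at each in-person visit has to be recorded so that it can be carried forward.
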